### **Aim 2**

Prior to randomization, the participant or participants' (for families enrolling more than one child) parent/legal guardian will complete a baseline questionnaire with demographic and COVID-19 mitigation behavior questions after providing informed consent/assent. Randomization will be conducted at the school-level. Participants in the intervention group will receive risk communication materials in the form of: (1) 3 comic books with accompanying read-along videos for children and (2) 2 videos for parents, once a month for three consecutive months. Participants randomized to the comparison group will be provided the same risk communication materials at the end of the school year as a delayed intervention. Parents of participants randomized to the Intervention group will be given two videos focused on COVID-19 topics such as testing and

vaccination throughout the school year. Similarly parents of participants randomized into the comparison group will receive the two videos as a delayed intervention. Throughout the duration of the study, participants will receive weekly brief email or text message reminders to complete an online Weekly Check-in Survey that collects information about COVID-19 symptoms, school absenteeism, and SARS-CoV-2 exposure. Parents of students who report that their child is experiencing COVID-19 symptoms will then be prompted to answer more questions about the illness, and any healthcare that they may have received. At Post Survey 1 and Post Survey 2 assessments, parents will be asked to complete a short online survey to update their demographic information, child's COVID-19 vaccination status, and the child's SARS-CoV-2 mitigation behaviors.

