**Follow-up (Post 1 and Post 2) Behavior Update Surveys:** At the end of the study, parents will be asked to complete the first post survey either online or by phone. The surveys will ask for updates to their contact and demographic information, child's COVID-19 vaccination status, and child's SARS-CoV-2 mitigation behaviors. For students with missing or phone numbers no longer in service, ROSSEY staff will contact the YSD to 1) determine if the student is still attending YSD 2) find out which school and teacher to send a notice to the parent. Sealed letters, requesting updating contact information, will be sent to the school for the teacher to send home with the student. Students determined to still be enrolled at YSD, and are non-responders to the follow up survey, will receive an at home follow up visit by ROSSEY staff as a final attempt to reach student and parent to complete survey. Follow-up assessment closure will take place one week after completion of home visits.

**Risk Communication:** Risk communication, in the form of printed comic books and accompanying read-along videos for the children (n=3), and videos for the parents (n=2), will be distributed in English and Spanish once a month after enrollment closes to children and their families randomly selected into the intervention group. For children and families in the control group, the same materials will be shared at the end of the study. Comic books will be distributed to the students by mail and parents will be mailed a password protected link to access the online health education videos and comic book read along videos.

The risk communication will highlight benefits and address barriers around preventive behaviors, such as SARS-CoV-2 testing and COVID-19 vaccination. The comic book will follow the main characters (siblings Hector, Mia, and Ava) and their experiences during the COVID-19 pandemic. The comic books will be narrated into videos for children with limited reading abilities and whose parents and/or siblings cannot read the comic books to them (this is what we refer to as "read

along” videos). The messages in the risk communication will be infused with constructs from the Health Belief Model, Social Cognitive Theory, Transtheoretical Model of stages of change and the Self Determination Theory.

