## 2. Study Schema and objectives

[figure not shown]
Purpose:	To determine the effectiveness of risk communication for parents and students on students' attendance to school, COVID-19 testing and vaccine uptake
Design:	A clustered randomized controlled trial of risk communication intervention
Central Hypotheses:	Our central hypotheses are that students and parents who view the risk communications will be more likely to have less school absence, increased covid-19 testing and vaccine uptake.
Primary Objectives:	

• To determine if implementing three COVID-19 education comic books for children and two COVID-19 education videos for parents will lower school absenteeism, increase COVID-19 testing, and vaccine uptake in children.

Secondary Objectives:	

• To determine if implementing three COVID-19 education comics books for children and two COVID-19 education videos for parents will increase physical activity, improve sleep, increase emotional regulation in children.

• To determine if implementing three COVID-19 education comics books for children and two COVID-19 education videos for parents will increase physical activity, improve sleep, decrease depression and anxiety in parents

Population:	Children ages 5-13 enrolled in kindergarten to 5 th grade in Yakima School District
Study Size:	14 schools randomized; 7 to intervention and 7 to comparison arms with 450 children in each arm; a total of 900 children from 14 schools.
Primary Outcome Measurements:	

A. Attendance captured through the school district

B. COVID-19 testing data available through the school district testing program and self-reported survey

C. COVID-19 vaccine data available through self-reported survey

Study Duration:	2 years including enrollment period, 2 months to deliver the intervention, 5 months for post 1 survey, 7 months weeks for post 2 survey.

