## 7. Outcome Definitions

### a. Primary Outcomes

The three co-primary outcomes for the trial are school absenteeism, COVID-19 testing, and COVID-19 vaccine uptake. Absenteeism are the student's school attendance data for 2022-2023 school year, COVID-19 data are captured through school testing and self-reported survey, and COVID-19 vaccine uptake data are captured through self-reported survey. All children and parent data after randomization will be included in the intention to treat analysis.

**Absenteeism:** total number of school days missed by each individual student participant, both for the entire school year and month-by-month, as captured and shared with us by school district administrative data systems. Absenteeism will also be measured by school days missed and will be a count variable.

**COVID-19 testing:** Health reports from the school are provided for the 2021-2022 and 2022-2023 school year that list positive covid test results of study participants with the date of testing and the school of attendance. Positive COVID test results will be a binary yes/no variable.

**COVID-19 vaccine uptake:** Parents are asked at enrollment to report their vaccination status and their child's vaccination status. At post survey 1 and post survey 2 the parent is asked to report if they or their child have received any COVID-19 vaccine or booster since enrollment. Vaccination status will be a binary yes/no variable.

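### The vaccine-uptake window opens at enrolment, before any material is sent, so doses the intervention could not have prompted can count as uptake and may dilute the arm difference

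*SAP*

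**What the plan says.** **Status of the outcome.** SAP 7.a: "The three co-primary outcomes for the trial are school absenteeism, COVID-19 testing, and COVID-19 vaccine uptake". The Protocol Summary lists vaccination as a secondary outcome; this point follows the SAP.

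**How it is measured.** At baseline, "Parents are asked at enrollment to report their vaccination status and their child's vaccination status". At Post 1 and Post 2 the parent is "asked to report if they or their child have received any COVID-19 vaccine or booster since enrollment". The coding rule is "Vaccination status will be a binary yes/no variable". No dose date is mentioned, although the same section does record a date for positive tests.

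**When exposure starts.** Protocol III, Aim 2: "Prior to randomization, the participant or participants' (for families enrolling more than one child) parent/legal guardian will complete a baseline questionnaire". Protocol V, Risk Communication: materials go out "once a month after enrollment closes to children and their families randomly selected into the intervention group". The Figure 1 timetable agrees.

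**Which data are analysed.** SAP 7.a: "All children and parent data after randomization will be included in the intention to treat analysis". SAP 12.c.ii uses a mixed logistic model for vaccine uptake, with no stated adjustment for baseline vaccination and no restriction to children not yet vaccinated.

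**Duration.** SAP 2 gives "2 years including enrollment period, 2 months to deliver the intervention, 5 months for post 1 survey", followed by a Post 2 survey at 7 months. The length of enrolment is not stated.

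**The concern.** Every family has a stretch of time inside the outcome window when nothing had yet been sent to anyone. It is longest for families who enrolled first. A child unvaccinated at enrolment and dosed while other families were still being recruited is scored as uptake, although no comic or video could have prompted that dose.

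Neither safeguard in the SAP removes such doses. The enrolment report does not, because the child was unvaccinated then and has a dose since. The intention-to-treat sentence does not, because a survey answered after randomisation still reaches back to enrolment.

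Such doses add the same background to both arms. That can pull the odds ratio towards 1 and cost power on a co-primary outcome. If enrolment dates differ between schools, unequal windows also add between-school variation, with only seven schools per arm.

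**Working it through.** **Inputs from the SAP (sections 2 and 4).** 7 schools and 450 children per arm; ICC 0.05; type I error 0.05 (taken as two-sided); a 20-point difference in vaccination rates; stated power 80%.

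**Inputs assumed.** Control and intervention rates of 30% v 50%, and the share q of children dosed between enrolment and first distribution. Neither is in the documents.

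**Step 1: reproduce the plan's figure.**
- Children per school: 900/14 = 64.3.
- Design effect: 1 + (64.3 − 1) × 0.05 = 4.16.
- Effective n per arm: 450/4.16 ≈ 108.
- Standard error at 30% v 50%: √[(0.30×0.70 + 0.50×0.50)/108] = 0.0652.
- Non-centrality: 0.20/0.0652 = 3.07. A non-central t with 14 − 2 = 12 df gives power of 80.3%.

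The same method gives 78.7% at 40% v 60% and 80.3% at 50% v 70%. The stated 80% is therefore reproduced for control rates of about 30–50%.

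**Step 2: add early doses when the 20-point effect applies to children not dosed early.** Recorded uptake in each arm is q + (1 − q)p, so the recorded difference is 20(1 − q) points.

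| q | Recorded rates | Difference (points) | OR | Power |
|---|---|---|---|---|
| 0 | 30.0% v 50.0% | 20 | 2.33 | 80.3% |
| 5% | 33.5% v 52.5% | 19 | 2.19 | 75.1% |
| 10% | 37.0% v 55.0% | 18 | 2.08 | 69.8% |
| 20% | 44.0% v 60.0% | 16 | 1.91 | 59.2% |
| 30% | 51.0% v 65.0% | 14 | 1.78 | 49.1% |

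**Step 3: the alternative, in which the whole-population difference stays at 20 points.** Early dosers take no further dose, and recorded uptake is q + p. At 30% v 50% power is 79.1%, 78.7%, 80.3% and 85.4% for q = 5, 10, 20 and 30%, so nothing material is lost. This requires a larger effect among children not dosed early: 20/(1 − q), which is 22 points at q = 10% and 25 at q = 20%.

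**Step 4: which q is plausible?** If 30% over 5 months also held before distribution, gaps of 1, 2 and 3 months give q = 1 − 0.70^(1/5), 1 − 0.70^(2/5) and 1 − 0.70^(3/5), or about 7%, 13% and 19%. At 10% over 5 months the figures are about 2%, 4% and 6%. In that low-uptake setting (10% v 30%) power goes from 93.6% to 85.3% at q = 6%.

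The SAP's two-year total would leave 24 − 2 − 5 − 7 = 10 months for enrolment if the phases run in sequence, or 24 − 7 = 17 if the surveys share one origin. This is inference only. SAP 4 places enrolment within the 2022–2023 school year, which suggests a shorter period.

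**Step 5: what a remedy recovers, in the setting of Step 2 with no second dose for early dosers.**

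| q | Current window | Early doses dropped from the numerator only | Children dosed early removed from the at-risk set |
|---|---|---|---|
| 10% | 69.8% | 73.1% | 79.3% |
| 20% | 59.2% | 65.2% | 78.1% |

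Dropping the early doses leaves rates of (1 − q)p, so the difference is still 20(1 − q) points and only 3 to 6 points of power return. Nearly all of it returns when the at-risk set is also redefined.

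**The case against.** The strongest reply is that the effect on the result is conditional. Step 3 shows that under another reasonable assumption the difference does not shrink, and the odds ratio can even rise (at 40% v 60%, from 2.25 to 2.33 at q = 10%). This stands. A reader might infer that the wording necessarily shrinks the co-primary difference; the documents do not establish that.

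The magnitude also rests on assumptions. The rows at 20% and 30% have no support in the documents, and with low uptake the power stays above 80%. This stands too.

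A reader might further infer that the comparison is biased or the test invalid. It is not: schools are randomised, so early doses are balanced in expectation and the type I error is unaffected. Nor does the SAP break a rule of its own. The intention-to-treat sentence says which data are included; it does not say that earlier events are excluded.

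Randomisation timing is not settled either. The Protocol's randomisation plan places it both upon enrolment and once the study launches, so the gap between enrolment and randomisation is uncertain. The gap between enrolment and first material does not depend on this.

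Finally, the binary status could mean ever vaccinated, in which case asking about doses since enrolment simply completes the baseline report. The SAP leaves this open. That reading does not help, because children vaccinated before enrolment would then count as well.

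**Conclusion.** The point holds in a limited form. On the since-enrolment reading, the stated window admits doses that precede any material, over a period that varies with enrolment date, and no stated analysis step removes them. This can dilute the arm difference and the planned 80% power without favouring an arm. At an assumed 30% v 50%, the cost is about 5 points of power at 5% dosed early and about 10 points at 10%, provided the 20-point effect applies to children not dosed early. It is close to nil if the whole-population difference stays at 20 points. On the ever-vaccinated reading, the same problem extends to doses before enrolment. The plan should be changed, but this is a matter of precision and interpretability, not of validity.

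**What to change.** 1. In SAP 7.a, define child vaccine uptake as a dose on or after one calendar date common to both arms of each pair: the randomisation date or the date of first distribution. If the distribution date is chosen, confirm that nothing specific to an arm reached families between randomisation and that date.
2. Keep the survey item that reaches back to enrolment and add the month of each dose. Asking only about doses after the new date would lose the interval needed to bring baseline status up to date.
3. Use doses between enrolment and that date to update baseline status. In SAP 12.c.ii, either adjust the mixed logistic model for the updated status or analyse children not yet dosed at that date. This step matters: removing early doses from the numerator alone recovers little.
4. Much of the SAP's missing-data section is written in the past tense, so data collection may be over. If the surveys are closed and hold no dose dates, adjust for vaccination status at enrolment, add a sensitivity analysis in families who enrolled shortly before enrolment closed, and state that the estimate includes pre-intervention doses.

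**Cost.** One survey field and a few SAP sentences. The price is some recall error in dose month, and fewer events or a slightly smaller at-risk set. The late-enroller analysis would use an unknown, possibly small, share of the sample.

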### Study Timeline

## 4. Sample size and power

**For month 5 outcome.** We will enroll 900 elementary school students from 14 schools in the Yakima School District during the 2022-2023 school year. The sample size of 7 schools per study arm and an average of 50 students per school will provide 90% power to detect a difference of at least 4 hours per week ( $SD=8.0$ ) of in-person school attendance between the intervention and control groups, while assuming intra-cluster correlation (ICC) of 0.05 and type I error rate of 0.05. The estimated sample size of 14 schools with 900 students provides 80% power to detect a difference of 20% or more in COVID-19 vaccination rates between the two study arms, assuming ICC of 0.05 and type I error rate of 0.05.

Minimum detectable difference in hours per week between intervention arms in proposed cluster RCT assuming enrollment of 15 students per classroom, 80% power and two-sided type I error rate of 0.05.					
		Two Arm			
	Number of clusters per arm	30		40	
	ICC	.01	.10	.01	.10
Standard Deviation	5.0	1.0	1.5	.87	1.3
	7.5	1.5	2.2	1.3	1.9

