## 6. Presentation of comparative analyses

For each of the continuous outcomes (including the primary outcome), the mean and standard deviation for each allocated group will be presented, together with the mean between-group difference, 95% confidence interval for the difference and p value. For binary outcomes, the percentage and frequency of children in the outcome category of interest (e.g. percentage vaccinated) will be presented for each allocated group, along with the odds ratio for the intervention effect, 95% confidence interval for the odds ratio and p value.

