### *Inferential Analyses:*

To determine if absenteeism differs between participants given COVID-19 educational material and the participants in the control group, we will conduct a complete-case analysis to compare mean absences between the intervention and control groups using a two-sample t-test.

We hypothesis implementing three COVID-19 education comic books for children and two COVID-19 education videos for parents will lower child's absenteeism and COVID infection rates and increased vaccine uptake.

School days missed will be modelled by a mixed zero inflated negative binomial model, with school specific random effects to account for clustering. COVID positive testing results will be modelled by a mixed logistic regression model, with school specific random effects to account for clustering.

Vaccine uptake will also be analyzed by mixed logistic regression model.

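### The co-primary vaccine-uptake outcome has no scoring rule and makes no use of the child's vaccination status at enrolment, which costs power under either reading

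*SAP*

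**What the plan says.** SAP section 7.a states: "The three co-primary outcomes for the trial are school absenteeism, COVID-19 testing, and COVID-19 vaccine uptake". The primary objective in SAP section 2 concerns uptake in children.

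The data come from two kinds of question. The enrolment survey covers vaccination status for the parent and, separately, for the child. The follow-up item, used in both later surveys, is about doses rather than status: "the parent is asked to report if they or their child have received any COVID-19 vaccine or booster since enrollment". The rule for deriving the analysed variable from these answers is a single sentence: "Vaccination status will be a binary yes/no variable". Section 7.a does not say how a child vaccinated before enrolment is scored, whether a booster alone counts, or which post survey supplies the co-primary result. Section 4 labels its power paragraph as being for month 5.

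Elsewhere the SAP uses status language. Section 6 gives "e.g. percentage vaccinated" as its example of a binary outcome, to be reported with an odds ratio. Section 4 claims "80% power to detect a difference of 20% or more in COVID-19 vaccination rates", with 14 schools, 900 students, ICC 0.05 and a type I error rate of 0.05.

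The model is named in section 12.c.ii, Inferential Analyses: "Vaccine uptake will also be analyzed by mixed logistic regression model". It has no baseline vaccination covariate and no restriction to unvaccinated children. The Aim 2 enrolment criteria (protocol section IV) do not exclude vaccinated children.

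**The concern.** The aim is to learn whether the materials lead to new vaccination. The plan collects what is needed to separate new doses from old ones, then does not say whether it will do so. Two scorings fit the text.

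- **Ever vaccinated.** A child vaccinated before enrolment is a *yes* in either arm and cannot respond. A booster in that child changes nothing. The wording of sections 4 and 6 leans this way.
- **Dose since enrolment.** A previously vaccinated child scores *no* unless boosted. The word uptake and the follow-up question lean this way. The comparison is sound, but the model omits what is probably the strongest available predictor.

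At stake is the power of one of three co-primary comparisons. A co-primary with two admissible scorings could also be settled after the data are seen.

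**Working it through.** **Inputs from the SAP.** 7 schools and 450 children per arm (section 2), so m = 900/14 = 64.3 per school; ICC 0.05, type I error 0.05 and a 20-point difference (section 4). Two-sided testing is stated only in section 4's hours-per-week table and is assumed here.

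**Inputs not in the documents (assumptions).** The control vaccination rate; v, the share of children vaccinated before enrolment; new uptake of 30% against 50% among the others; no boosters, in the since-enrolment calculation.

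**Step 1: reproduce the stated 80%.** Design effect = 1 + (64.3 − 1) × 0.05 = 4.16. Effective sample size per arm = 450/4.16 = 108.1. For 30% against 50%, SE = √[(0.30 × 0.70 + 0.50 × 0.50)/108.1] = 0.065, and 0.20/0.065 ≈ 3.07. A noncentral t with 14 − 2 = 12 degrees of freedom gives power 80.3%. For 40% against 60% it gives 78.7%. The stated figure therefore reproduces when the analysed rates lie near 50% and the full 20 points appear in the analysed variable.

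**Step 2: put prior vaccination into the outcome.** Let c and t be new uptake among children unvaccinated at enrolment.

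- Ever vaccinated: the rates are v + (1 − v)c and v + (1 − v)t, so the difference is (1 − v)(t − c).
- Dose since enrolment, no boosters: the rates are (1 − v)c and (1 − v)t, so the difference is the same.
- Children unvaccinated at enrolment only: c against t, with m(1 − v) children per school.

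With c = 0.30, t = 0.50, and power from the same t calculation:

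| v | Difference, all children | Ever vaccinated: rates | Power | Since enrolment: rates | Power | Unvaccinated only: power |
|---|---|---|---|---|---|---|
| 0.1 | 18 points | 37% v 55% | 69.8% | 27% v 45% | 73.1% | 79.3% |
| 0.3 | 14 points | 51% v 65% | 49.1% | 21% v 35% | 56.9% | 76.6% |
| 0.5 | 10 points | 65% v 75% | 31.8% | 15% v 25% | 39.9% | 71.9% |

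Without boosters the absolute difference shrinks equally under both scorings. The since-enrolment outcome keeps somewhat more power because its rates are further from 50%. Most of the loss disappears when the analysis knows which children were unvaccinated at the start.

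**Step 3: chance baseline differences.** If enrolment status also has ICC 0.05 (an assumption), the SD of the between-arm difference in v is √[2v(1 − v)/108.1]. This is 6.2 points at v = 0.3 and 6.8 points at v = 0.5. By the normal approximation, a gap of 10 points or more arises in about 11% and 14% of randomisations. The calculation ignores any gain from matching schools on English Language Learners and size (protocol section V, RCT Randomization Plan).

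**The case against.** The strongest reply is that section 7.a already describes a new-dose outcome. The outcome is called uptake, the follow-up question is about the period since enrolment, and the variable sentence comes straight after it. The percentage in section 6 is only an example, and the rates in section 4 could be rates of new vaccination. This stands as a fair alternative reading. A reader might infer that children vaccinated before the trial are certain to count as successes. The documents do not say so; that holds only under the ever-vaccinated reading.

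A reader might also infer that chance imbalance in baseline coverage biases the result. Under randomisation it does not. It is sampling variance, and at a given rate the SD in step 3 is the same quantity that the ICC-based power calculation already carries. What remains is that the variance could be reduced by adjustment and the plan does not do so.

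Third, a parent's own booster might seem able to score as a *yes* for the child, because one question covers both. That is speculative. Section 7.a lists parent and child status separately at enrolment, section 2 sets the objective in children, section 6 reports on children, and the protocol's follow-up surveys ask for the child's status.

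Finally, the size of the loss depends on v, which the documents do not give. At v = 0.1 it is modest.

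**Conclusion.** The co-primary vaccine outcome lacks a scoring rule, and nothing in the outcome definition, analysis set or model uses the child's enrolment status, although it is collected. Under the ever-vaccinated reading, a 20-point effect among unvaccinated children becomes 20 × (1 − v) points, and power falls to about 70%, 49% or 32% at v = 0.1, 0.3 or 0.5. Under the since-enrolment reading the comparison is valid; the cost is lost precision and unadjusted chance differences with an SD of about 6 to 7 points. These figures rest on assumed coverage, 30% against 50% new uptake, ICC 0.05 for both outcome and baseline status, and 12 degrees of freedom.

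The documents do not support calling this a demonstrated dilution or a systematic bias. It is a free or cheap improvement, not an error that must be fixed.

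**What to change.** In SAP section 7.a, define the co-primary as the child receiving at least one COVID-19 vaccine or booster dose since enrolment, assessed at one named post survey. In section 12.c.ii, add the child's enrolment vaccination status as a covariate in the mixed logistic model and state that the model has school random effects. Do not use that covariate with an ever-vaccinated outcome: every child vaccinated at enrolment would be a *yes*, so it would predict *yes* perfectly.

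Report first doses among children unvaccinated at enrolment as a supporting result. In section 4, state that the 20-point target refers to the new-dose outcome. The new definition does not by itself restore 20 points across all children, because previously vaccinated children contribute only through boosters. The gain from the covariate was not calculated, since it depends on booster rates that the documents do not give.

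The cost is SAP wording and one covariate already collected, with no new data. Cumulative vaccination status becomes descriptive only, and the adjusted odds ratio must be read as conditional on enrolment status.
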